Patients were randomized into two groups: Group 1 received SSNB at the spinoglenoid notch level, while Group 2 received SSNB at the suprascapular notch level. Stratified randomization was performed in four blocks based on age and gender. Group allocations were made (using sealed envelopes) by our medical secretary. The assigned numbers were presented to the physician at the time the procedure was performed. The patients and the physician assessing the outcomes were blinded to the group assignments, but the physician who performed the injections could not be blinded.

Procedures

All injections were administered by a single experienced physician specializing in musculoskeletal injections who used the linear transducer (LA3-16AD) of the Samsung HM70A Plus US device (Seoul, South Korea). The same injection solutions were prepared for both groups and consisted of 1 mL of methylprednisolone acetate (40 mg/mL) and 5 mL of 0.5% bupivacaine for the SSNB.

For SSNB at the level of the spinoglenoid notch, the patients were positioned on a stretcher in the lateral decubitus position between the US device and the physician. The patient's hand on the side of the injection was placed on the contralateral shoulder. The transducer was positioned on the glenohumeral joint, parallel to the inferior border of the spina scapula, and then shifted medially to visualize the spinoglenoid notch. After sterile prep, a 20G 3.5-inch needle was advanced, using an in-plane technique, into the spinoglenoid notch. A lateral-medial needle insertion was used so that the intended target of the final needle tip was at the medial wall of the spinoglenoid notch.

For SSNB at the level of the suprascapular notch, the technique described by Harmon et al.(1) was used. In brief, the patient was positioned seated between the physician and the US equipment. The patient's injection-side hand was placed on the shoulder on the opposite side. To view the suprascapular notch, the transducer was positioned above the acromion, parallel to the spina scapula, and then gently adjusted medially. After sterile prep, a 20G 3.5-inch needle was advanced into the suprascapular notch.

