shoulder ROM measurements of the patients were performed using a standard manual goniometer. Measurements were made in the supine position, and active forward flexion (FF), abduction (US), internal rotation (IR), and external rotation (ER) were measured. The IR and ER measurements were made with the shoulder abducted at 90°. The PPT measurements were obtained over the middle deltoid, upper trapezius, infraspinatus, and tibialis anterior muscles using a 1 cm diameter probe from an electronic digital display algometer (Commander Echo® Algometer, JTECH Medical, Midvale, UT, USA). Measurements were taken directly on the skin and vertically, and the patient was instructed to stop when the feeling of pressure first turned into a feeling of pain and discomfort. Three measurements were taken from each region, and the average of the last two measurements was recorded. The PPT values were expressed as kilograms per square centimeter (kg/cm²). A low PPT value represents a decrease in the pain threshold and, therefore, increased sensitivity. A 5-point Likert scale was used to evaluate the patients' overall satisfaction with the treatment (1= extremely dissatisfied, 2= dissatisfied, 3=neutral, 4= satisfied, and 5= extremely satisfied).

The patients' compliance with the exercise program was queried at the 4th and 12th weeks after the injection. The patients were asked to choose between "Never did," "I did it occasionally," and "I did it regularly." Finally, they were asked how much they used the paracetamol (500 mg) and naproxen (750 mg) that had been sent home with them after the injection at the 1st, 4th, and 12th weeks. The total amount of drug used was recorded.

Statistical Analyses

The sample size required for the research was calculated via a website (<http://statulator.com/SampleSize/ss2M.html>). In a previous study, the Minimal Clinically Important Difference (MCID) value for SPADI ranged from 8 to 13 points (2). We established our research hypothesis that the clinical results of SSNB at the level of the spinoglenoid notch would not be non-inferior to SSNB at the level of the suprascapular notch. Accordingly, when the non-inferiority margin is -9 and the standard deviation is 15.3; With 80% power and type 1 error 0.05, 36 patients in each group should be recruited. Assuming a 10% dropout rate, 40 patients were planned for each group.

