The collected data were statistically analyzed using IBM SPSS ver. 22.0 (IBM Corp., Armonk, NY, USA). All analyses were performed according to the "intention to treat" principle, and the missing data were completed using the single imputation method. The Shapiro-Wilk test, as well as histograms and QQ plots, were used to test whether the data were normally distributed. Analysis results were presented as mean \pm standard deviation for numerical data and as numbers and percentages for categorical data. For numerical data, the differences between groups were compared using the independent samples t-test or the Mann-Whitney U test. Categorical data were analyzed using chi-square tests or Fisher's exact test. In addition, the differences (Δ) between the baseline value of the outcome measures and the values at the follow-up time points were calculated and included in the intergroup comparison. The Friedmann test was used for intragroup comparisons of the changes in outcome measures from baseline to follow-up times. The post hoc Dunn-Bonferroni test was then used for

pairwise comparisons of follow-up times. A P value less than 0.05 was considered statistically significant.

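### A trial sized for non-inferiority is analysed only by intention to treat with an unnamed single imputation, with no check on whether departures or imputed values pull the arms together

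*Combined protocol and SAP*

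**What the plan says.** The sample-size paragraph of Statistical Analyses frames the trial as a non-inferiority comparison. The hypothesis is worded awkwardly (the spinoglenoid block "would not be non-inferior to SSNB at the level of the suprascapular notch"), but the calculation makes the intent clear: "when the non-inferiority margin is -9 and the standard deviation is 15.3". It continues: "With 80% power and type 1 error 0.05, 36 patients in each group should be recruited". Then: "Assuming a 10% dropout rate, 40 patients were planned for each group".

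The analysis paragraph of the same section says: "All analyses were performed according to the 'intention to treat' principle". Missing data are completed by single imputation, with no method named. Groups are compared by t-test or Mann-Whitney U test at P < 0.05. The section defines no per-protocol or as-treated set, no major protocol departure and no sensitivity analysis, and it compares no confidence interval with the margin.

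Outcome Measures records exercise compliance at weeks 4 and 12 ("The patients were asked to choose between 'Never did,' 'I did it occasionally,' and 'I did it regularly") and the total amount of analgesic used. Neither has a role in the analysis. Nothing is said about how another injection or surgery to the study shoulder during follow-up would be handled.

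**The concern.** In a superiority trial, keeping every randomised patient in the assigned arm is usually conservative, because departures tend to shrink the observed difference and make the claim harder. In a non-inferiority trial the same shrinkage makes the claim easier. Single imputation can act in the same direction if the method fills gaps with values that do not depend on arm.

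At stake is how far a reader could trust a non-inferiority conclusion. With one analysis set and one unnamed imputation, the report could not show whether the conclusion depends on patients whose treatment departed from the plan, or on values that were never observed.

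**Working it through.** **Inputs from the plan (Statistical Analyses).** Margin 9 SPADI points, SD 15.3, power 80%, type 1 error 0.05 with sidedness not stated, 36 per group, 10% dropout, 40 per group. "Deficit" below means the number of SPADI points by which the spinoglenoid arm is worse.

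**Step 1: reproduce the plan's figure.** With a true difference of 0 and one-sided 0.05:

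n = 2 × 15.3² × (1.645 + 0.842)² / 9² = 35.7, so 36 per group; 36 / 0.90 = 40.

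Both figures reproduce. One-sided 0.025 gives 46 and does not. The sample size is therefore consistent with its own inputs, and the trial is a non-inferiority design at one-sided 5%.

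**Step 2: how dilution affects the claim.** This needs assumptions that the plan does not supply: a margin test at one-sided 5%, a true deficit of exactly 9 points in patients treated as planned, a share f of each arm that departs and shows no arm difference at all, and an unchanged SD.

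SE = 15.3 × √(2/40) = 3.42

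P(declare non-inferiority) = Φ((9 − 9(1 − f)) / 3.42 − 1.645)

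| f | expected deficit | false non-inferiority |
|---|---|---|
| 0% | 9.0 | 5.0% |
| 5% | 8.55 | 6.5% |
| 10% | 8.1 | 8.4% |
| 20% | 7.2 | 13.2% |
| 30% | 6.3 | 19.6% |

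For example, at 10%: 0.9 / 3.42 = 0.263; 0.263 − 1.645 = −1.382; Φ = 0.0835.

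**Step 3: imputation.** The plan's only related rate is the 10% dropout allowance. Suppose 4 of 40 per arm are missing at random and each is filled with the mean of all observed patients, ignoring arm. In simulation, a true 9-point deficit is then declared non-inferior in about 8.5% of trials. Other single imputations would give other figures, and the plan does not say which applies.

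**Step 4: what a per-protocol repeat can deliver.** Power at a true difference of 0 is Φ(9 / (15.3 × √(2/n)) − 1.645).

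| evaluable per arm | power |
|---|---|
| 40 | 83.8% |
| 36 | 80.3% |
| 32 | 76.1% |
| 28 | 71.1% |

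The evaluable numbers are assumptions.

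**Step 5: the per-protocol set can also mislead.** Suppose the true deficit is 9 and the worst-scoring 10% of all patients are excluded, as might happen if treatment failures leave or are re-injected. The arms then lose about 5% and 15%, leaving roughly 38 and 34 patients with SDs of about 13.7 and 12.3. The deficit among those left is about 6.5 (6.54).

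SE = √(13.7²/38 + 12.3²/34) = 3.06; (9 − 6.54) / 3.06 − 1.645 = −0.84; Φ = about 20%.

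This too is a worst case, and here it exceeds the 8.4% in Step 2 at the same 10%.

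**The case against.** The strongest reply is that the usual route of dilution is nearly closed. Under Procedures, treatment is one ultrasound-guided injection, given by a single experienced physician with the same solution in both arms, and the assignment is shown when the procedure is performed. There is no continuing treatment to stop or switch, so delivery at the wrong notch should be rare. This stands, and it lowers the likely size of the problem.

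The figures in Step 2 can also be challenged. The documents give no departure rate. A patient who has had the assigned block and later leaves or receives other care need not lose the whole arm difference. The margin test behind the percentages is not in the plan, which names only tests of difference. All of this stands: the percentages are an upper illustration, not an estimate.

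A reader might infer that the exercise and analgesic records already supply what a per-protocol set needs. They do not. Analgesics were allowed as needed, and the exercise programme was prescribed in both arms, so neither by itself marks a departure from the assigned block. Analgesic use close to a visit would go against the plan's request, but only the total amount is recorded, not its timing.

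Finally, a per-protocol analysis excludes patients for events after randomisation, and Step 5 shows that this can favour non-inferiority more than intention to treat does. Agreement of the two analyses is therefore limited reassurance. That is a reason to make the second analysis supportive and to report exclusions by arm. It does not remove the case for having a check.

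**Conclusion.** The point holds as a gap in the analysis plan. The trial is sized for non-inferiority, its only analysis set is intention to treat with an unnamed single imputation, and nothing would show whether departures or filled-in values drive the result.

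Under the worst-case assumptions of Step 2, false non-inferiority rises from 5.0% to about 8.4% at 10% departures and 13.2% at 20%. The real effect is probably smaller and cannot be fixed from the documents.

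A reader might go further and conclude that a spinoglenoid block worse by the full margin is likely to be passed as non-inferior, or that intention to treat is the wrong primary analysis. The documents support neither. They report no departures, the single-injection design limits them, and intention to treat is the set that randomisation protects. Nor can a rule that both analyses must succeed be applied to the plan as written, because no criterion for non-inferiority is stated in either set.

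**What to change.** 1. State the non-inferiority test: compare the confidence interval for the between-group difference in week-12 SPADI with the 9-point margin in the intention-to-treat set. Give its level (one-sided 5% is what the sample size implies) and name the imputation method.
2. Repeat the same comparison as a supportive analysis in a per-protocol set: assigned block delivered at the assigned notch, no other injection or surgery to the study shoulder up to week 12, and week-12 SPADI observed.
3. Have the set defined by someone blind to allocation. The text is in the past tense; if the data are already unblinded, use the same objective criteria and label the analysis post hoc.
4. Report exclusions by arm and reason. If the two analyses disagree, describe the non-inferiority result as not robust.

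**Cost.** SAP wording and one repeat analysis; the planned 36 and 40 per group do not change. The downside is that the per-protocol set is smaller (power about 76% with 32 per arm), is not protected by randomisation, and can itself err toward non-inferiority if treatment failures are excluded. It therefore stands beside the intention-to-treat analysis and does not replace it.

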One week after the injection, all patients received a prescribed exercise regimen to be performed in their own homes. The exercise routine encompassed self-stretching, joint mobility exercises, and strength-building activities. A designated physical therapist demonstrated the exercises to each patient individually, and an exercise booklet was provided to assist them.

Finally, the patients were advised to use paracetamol (500 mg) and/or naproxen (750 mg), if necessary. They were asked not to take analgesics at or 1 day before the follow-up points, as it could affect the clinical outcome measures.

Outcome Measures

All patients were evaluated for primary and secondary outcome measures before injection (baseline) and at 1, 4, and 12 weeks after injection by an investigator blinded to the injections. The primary outcome measure of the study was the Shoulder Pain and Disability Index (SPADI), while the secondary outcome measures were visual analog scale (VAS) scores, active range of motion of the shoulder (ROM), pressure pain thresholds (PPT), and treatment satisfaction. All adverse events that occurred during the procedure and at a follow-up visit were recorded.

Primary outcome measure: The Shoulder Pain and Disability Index is a shoulder-specific index consisting of 13 items that assess shoulder pain and disability on two different scales. Each item is scored between 0 and 10, and the resulting score is converted into a 100-point scale separately for pain, disability, and total score. Increased SPADI scores indicate an increase in patients' shoulder-related pain and disability. Patients with a reduction in the total SPADI score of 18 points or more from baseline to week 12 (the last follow-up) were considered treatment successes. (2). The SPADI has been shown to be valid and reliable in Turkish (3).

Secondary outcome measures: The VAS (0–10 range) was evaluated in each patient for night and activity. An additional VAS assessment was performed 1 h after the injection. Active

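### Missing outcomes are filled by one unnamed single imputation and tested as if observed, with no supportive missing-data analysis; the effect is modest and depends on the fill

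*Combined protocol and SAP*

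**What the plan says.** Missing data are covered by one clause of the Statistical Analyses section, in the sentence that commits all analyses to intention to treat: "the missing data were completed using the single imputation method". The technique is not named, and nothing says whether it works within arm or on the pooled sample. For numerical outcomes, "the differences between groups were compared using the independent samples t-test or the Mann-Whitney U test". Changes "between the baseline value of the outcome measures and the values at the follow-up time points were calculated and included in the intergroup comparison". No complete-case, repeated-measures, multiple-imputation or delta-adjusted analysis is described.

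The same section expects losses: "Assuming a 10% dropout rate, 40 patients were planned for each group". The sample size is set "when the non-inferiority margin is -9 and the standard deviation is 15.3".

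Under Outcome Measures, "All patients were evaluated for primary and secondary outcome measures before injection (baseline) and at 1, 4, and 12 weeks after injection". The responder definition turns on this wording: "reduction in the total SPADI score of 18 points or more from baseline to week 12 (the last follow-up) were considered treatment successes".

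**The concern.** A single imputed value carries no information about its own uncertainty, and the listed tests cannot supply it. If the fill sits at the centre of its arm, the standard error is too small. If the fill is far from the observed values, as baseline is after improvement, the standard error is too large. If the fill ignores arm, or is much the same in both arms, it pulls the arms together. Because the plan does not say which fill is used, a reader cannot tell whether a reported P value is too small, about right or too large.

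The sample size rests on a non-inferiority margin, so pulling the arms together favours the claim under study. The responder endpoint is exposed too: baseline carried forward sets the week-12 change to zero, so every dropout becomes a failure under the 18-point definition.

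**Working it through.** **Inputs from the plan.** Margin 9, SD 15.3, 80% power, alpha 0.05, 36 per group, 10% dropout, 40 per group (Statistical Analyses); SPADI at baseline and weeks 1, 4 and 12 (Outcome Measures).

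**Assumed.** Normal scores; SPADI means of 60, 40, 35 and 30 at baseline and weeks 1, 4 and 12; correlation 0.5 between visits; only week 12 missing, 4 of 40 per arm; comparison at week 12; a two-sided 5% difference test (the plan gives P < 0.05 without sidedness); pooled-variance t-test on the completed data.

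**Plan's own figure.** 2 × [15.3 × (1.645 + 0.842)/9]² = 35.7, so 36 per group, and 36/0.9 = 40. This reproduces at one-sided 5%. With 1.960 the result is 45.4, so 46.

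**Step 1: arm-mean fill, week-12 score.** True SE = 15.3 × √(2/36) = 3.61. The completed data report this multiplied by √[(35/39) × (36/40)] = 0.899, so 3.24. The two-sided error is 2 × [1 − Φ(1.96 × 0.899)] = 7.8%; simulation gives 7.9%.

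**Step 2: baseline carried forward.** Four values lie 30 points from the other 36 on average, so the completed variance is about 15.3² + (36 × 4/40/39) × 30² = 234.1 + 83.1 = 317.2. Reported SE = √(2 × 317.2/40) = 3.98; true SE = √(2 × 234.1/40) = 3.42. The error is 2 × [1 − Φ(1.96 × 3.98/3.42)] = 2.3%, and simulation agrees.

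**Step 3: all fills, two-sided 5%, no true difference, random dropout (simulated).**

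| Fill | Rejects |
|---|---|
| Arm mean | 7.9% |
| Regression within arm | 6.6–7.1% |
| Pooled mean | 5.0% |
| Pooled regression | 5.0% |
| Week 4 carried forward | 4.9% |
| Baseline carried forward | 2.3% |
| Complete case (no fill) | 5.0% |

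**Step 4: change from baseline (Δ), week-12 score filled by the arm mean.** At correlation 0.5, Δ has the same SD as the score. The true variance of an arm's mean Δ is σ²(1/36 + 1/40 − 2 × 0.5/40) = σ²/36, and the reported variance is about σ²/40. The SE ratio is √0.9 = 0.949 and the error 2 × [1 − Φ(1.96 × 0.949)] = 6.3%. Simulations give about 6% to 6.5%.

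**Step 5: a true difference of 9.** Pooled-mean fill gives 0.9 × 9 = 8.1, and baseline fill also gives 0.9 × 9 + 0.1 × 0 = 8.1. Pooled regression gives 8.6 (simulated, with a difference of 9 at weeks 1 and 4). Week-4 carry-forward gives 0.9 × 9 + 0.1 × (week-4 difference): 9.4, 9.0, 8.5 or 8.1 for week-4 differences of 13, 9, 4.5 or 0.

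**Step 6: if judged against the margin.** One-sided 5%, true deficit 9, chance of false non-inferiority, 4 versus 4 missing. In the right-hand column, Group 1 leavers average 18 points worse than their arm at week 4 and Group 2 leavers are random. Ranges span repeated simulations.

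| Method | Random dropout | Week-4-dependent, one arm |
|---|---|---|
| Complete case | 5.1% | 8.4–8.7% |
| Arm mean | 6.6–6.9% | 11.3–11.6% |
| Pooled mean | 8.2–8.5% | 13.6–14.0% |
| Regression within arm | 6.0–6.4% | 6.2–6.5% |
| Pooled regression | 6.4–6.6% | 6.7–6.9% |
| Baseline carried forward | 5.5–5.6% | 5.0–5.2% |
| Week 4 carried forward | 4.8–4.9% | 2.0–2.5% |
| Mixed model | 4.6% | 4.5% |
| Multiple imputation | 4.6% | 4.8% |

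Monte Carlo error is about 0.1 points in the largest runs (40,000 trials) and about 0.3 in the smaller ones (5,000 to 8,000), which include the mixed model and multiple imputation.

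**The case against.** The strongest reply is that this is a small matter of reporting. Four patients per arm is a planning allowance, not a count. Week-4 carry-forward, a natural choice with three follow-ups, is close to nominal under random dropout. Even a 9-point worsening of 4 imputed values moves an arm mean by only 4/40 × 9 = 0.9. All of this stands as to size. It does not make the plan adequate: a method is stated, it cannot be identified, and better use of the scores already collected at baseline and weeks 1 and 4 is available at little cost.

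Four stronger readings are tempting and are not supported.

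- A reader might infer that the error grows whenever dropout depends on earlier scores. In the setting above it grows for mean fills and complete case only; regression and baseline fills barely move, and week-4 carry-forward becomes conservative.
- A reader might infer that single imputation always favours non-inferiority. Week-4 carry-forward does not when the week-4 difference equals or exceeds that at week 12.
- The 7.9% might be read as applying to every test in the plan. It is for week-12 scores under a t-test; the Δ comparison gives about 6% to 6.5%, and Mann-Whitney was not simulated.
- The largest percentages might be read as error rates of the planned test. They belong to a test against the margin, which the analysis text does not state.

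One limit also applies to the remedy. The dependent dropout was generated from observed week-4 scores, the condition under which the mixed model and multiple imputation work. Dropout driven by the unseen week-12 value was not simulated for them, hence the delta-adjusted analysis in the fix.

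**Conclusion.** The point holds in a limited form. Completed data from an unidentified single imputation are tested as if observed, and no supportive analysis is planned. That no correction is applied is inferred from silence, but the listed tests have no means of making one.

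At the plan's own dropout allowance, the choice of fill alone moves a nominal two-sided 5% error between about 2.3% and 7.9%. Three of the six fills shrink a true difference of 9 to 8.1–8.6 under equal dropout, and week-4 carry-forward may do so. Margin-test errors of about 11% to 14% arise only with mean fills and one-sided, week-4-dependent dropout.

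These figures rest on the assumed means, correlation, normality, sidedness and week-12 comparison, and on exactly 4 of 40 missing per arm. If no outcome is missing, the effect is nil. The choice of primary time point, a confidence interval against the margin, and baseline adjustment are separate issues.

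**What to change.** For total SPADI, replace single imputation with one of two methods:

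- a likelihood-based mixed model for repeated measures using all observed scores at baseline and weeks 1, 4 and 12; or
- multiple imputation within arm from baseline, week 1 and week 4, combined by Rubin's rules.

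Derive responder status from multiple imputations of the same kind, so that dropouts are not made failures by construction. As supportive analyses, add complete case and a delta-adjusted multiple imputation that worsens imputed Group 1 values by 3, 6 and 9 points. With 4 of 40 imputed these shift the Group 1 mean by 0.3, 0.6 and 0.9. Report the number missing by arm and visit. If the single imputation is kept as a supportive analysis, name it and say whether it is done within arm.

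The cost is a little more analysis work, with no new visits or patients. Multiple imputation gives an SE of about 3.58 without baseline adjustment, so its interval is slightly wider than the 3.23 that arm-mean fill would report; the latter is too small against a true value of about 3.6. The plan names SPSS 22.0 but not whether the installation includes these procedures; if it does not, another package is needed.

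### The SPADI comparison is not fixed in advance: it may go to a t-test or to Mann-Whitney, and the rank test gives no mean difference to set against the 9-point margin the trial was sized on

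*Combined protocol and SAP*

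**What the plan says.** All of this is in the Statistical Analyses section of the combined protocol and SAP.

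- **Sizing.** The question is framed as non-inferiority on SPADI, "when the non-inferiority margin is -9 and the standard deviation is 15.3". The result follows: "With 80% power and type 1 error 0.05, 36 patients in each group should be recruited". Then: "Assuming a 10% dropout rate, 40 patients were planned for each group".
- **Normality.** "The Shapiro-Wilk test, as well as histograms and QQ plots, were used to test whether the data were normally distributed". No threshold is given, and no rule for weighing the plots against the test.
- **Between-group test.** Numerical data are "compared using the independent samples t-test or the Mann-Whitney U test". SPADI is not exempted, and changes from baseline are compared as well as visit values.
- **Reporting.** Results are shown as mean and "standard deviation for numerical data and as numbers and percentages for categorical data", whichever test was used.
- **Decision rule.** P below 0.05. The section describes no confidence interval and no test shifted by the margin.

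**The concern.** A margin of 9 SPADI points with an SD of 15.3 defines a question about a difference in means. The analysis text does not commit to a method that estimates that difference. Mann-Whitney tests whether values in one arm tend to be larger than in the other. It could address a 9-point shift only if one arm were first shifted by the margin, or if a Hodges-Lehmann interval were used under an equal-shape assumption, and neither is planned. After a switch, the reported means and the reported P value would describe different quantities.

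Because the choice is made on the collected data, partly by eye, the test could also differ between weeks 1, 4 and 12 and between raw and change scores of the same primary outcome. At stake is whether the report contains a number that can be compared with the margin.

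**Working it through.** **1. The plan's own sample size.** Margin 9, SD 15.3, power 80% and type 1 error 0.05 are stated. The sidedness and the true difference are not; one-sided and 0 are assumed.

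n per group = 2 × (SD/margin)² × (z₁₋α + z₀.₈₀)²

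- One-sided 0.05: 2 × (15.3/9)² × (1.645 + 0.842)² = 35.7, so 36. With dropout, 36/0.90 = 40. Both stated figures are reproduced.
- One-sided 0.025: 2 × (15.3/9)² × (1.960 + 0.842)² = 45.4, so 46. This does not reproduce.

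The stated 36 and 40 are therefore a comparison of means at one-sided 0.05, which corresponds to a 90% two-sided interval.

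**2. How often the check would point away from the t-test.** Shapiro-Wilk at 0.05 is applied in each arm, and a switch is counted if either arm fails. For normal data and two independent arms, 1 − 0.95² = 9.75%, and simulation agrees (about 10%). The documents give no SPADI means, so the week-12 mean is an assumption shown over a range. The simulation has 40 per group, scores clipped to 0–100 and an assumed visit correlation of 0.5.

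| Week-12 raw SPADI, SD 15.3 | At least one arm fails |
|---|---|
| assumed mean 40 | about 8% |
| assumed mean 35 | about 8% |
| assumed mean 30 | about 10% |
| assumed mean 22 | about 38% |
| assumed mean 15 | about 96% |

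The week-12 change score fails in about 9% to 10%. This covers Shapiro-Wilk only; the histograms and QQ plots have no stated rule and cannot be simulated.

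**3. What a P value against zero says at the margin.** Two-sided tests against zero, 36 per group, SD 15.3, true difference exactly 9 points, 4,000 trials per shape. The shapes are assumptions.

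| Shape | Mann-Whitney not significant | t-test not significant |
|---|---|---|
| normal | 33% | 30% |
| gamma, shape 4 | 26% | 31% |
| gamma, shape 2 | 17% | 30% |
| uniform | 36% | 32% |

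Neither test, used this way, can establish non-inferiority. The difference is that the t-test comes with an estimated mean difference and an interval, and Mann-Whitney does not.

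**4. Whether a mean-based analysis needs the check.** In the same simulations, a one-sided t-test at 0.05 against the 9-point margin gave the following:

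- Non-normal shapes: type I error at the margin 4.6% to 5.2%, power 79.6% to 80.2%.
- Normal data: 4.4% and 79.1%.

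The Monte Carlo standard error near 5% is √(0.05 × 0.95/4000) = 0.3 percentage points. The t-based analysis held up under these shapes without a normality check.

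**The case against.** The strongest reply is that the switch is not what loses the answer on the margin. As written, the t-test also tests only zero, and step 3 shows it is non-significant about as often as Mann-Whitney at a true 9-point difference. That stands. The more basic gap is that no interval is compared with the margin. The point here is narrower: one permitted route yields that interval directly and the other does not.

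Three further replies stand in part.

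- **The link is implied.** The section never says that the normality result selects the test. No other purpose is given for the check, and if it does not select the test then nothing does. The same fix applies either way.
- **The effect on the test of zero is small.** With no true difference, choosing the test by the check gave a type I error of 4.9% to 5.4% over 4,000 trials per scenario, and the two tests disagreed on significance in only about 1.5% to 1.7%.
- **The change score usually stays with the t-test**, at about 90% in these simulations.

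A reader might infer that a switch is the likely outcome. The documents do not support that. A failure rate of 86% for week-12 raw SPADI needs an assumed mean of 22 and SD of 20, whereas the only SD in the plan is 15.3. It is also true that at least one of 12 checks (2 arms × 3 visits × raw and change) fails in about 47% of trials with normal data. That says some visit may use a different test; it is not the chance that the primary comparison switches. Nor do the documents show that the choice was steered by the results; they only leave room for it.

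**Conclusion.** The point holds in limited form. The SPADI comparison is not fixed, and one of the two permitted tests gives no mean difference to set against the 9 points on which the 36 (40) per group rest. The section must be tightened on this, but it is not evidence of a wrong result.

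The size depends on values the documents do not give. For week-12 raw SPADI the chance of failing the check is about 10% under normality and about 8% to 96% with SD 15.3 and a floor at 0. It rises steeply only when the assumed mean falls below about 30. For the change score it is about 10%. These figures assume Shapiro-Wilk at 0.05 in each arm, 40 per group, and that failure in either arm triggers the switch. Week 12 is used because it is the last follow-up and the visit at which treatment success is defined.

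A reader might go further and conclude that the planned analysis gives no answer once SPADI is skewed. That is too strong: the t-test route, and the change score in most cases, would still allow a mean-difference interval to be computed.

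**What to change.** State in the Statistical Analyses section that SPADI is compared as a difference in means with a t-based or model-based confidence interval (for example, ANCOVA adjusted for baseline), whatever the normality check shows. Use a 90% two-sided interval, matching the one-sided 0.05 that reproduces the sample size, and set it against the 9-point margin. Name the visit, and state the direction: higher SPADI is worse, so for spinoglenoid minus suprascapular the upper limit must lie below +9. Keep rank-based or bootstrap results as sensitivity analyses only. Naming one test for each secondary outcome is optional, since no margin applies there.

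The cost is a few sentences and a few lines of analysis. The sample size does not change: with 36 per group the power is 80.3% by the normal approximation and 79.6% by the noncentral t, and with 40 it is 83.8% and 83.2%. No new data are needed. The document is written in the past tense; if the data have already been analysed, the interval can still be computed and reported, with a note that it was specified afterwards.
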